4.3 Sub-Study Design and Scope

This sub-study will determine the incidence of externalized conductors and other visual lead anomalies (as evidenced by imaging) and the risk of progression to electrical dysfunction in patients implanted with an Optisure HV lead. A minimum of 200 subjects who consent to participate in this sub-study will undergo cinefluoroscopy (AP, LAO 45° or the best possible LAO view, RAO 45° or the best possible RAO view) at the 24, 36, 48 and 60 month follow-up visits.

Expected Attrition in patients with high voltage leads

Withdrawals due to death

[figure not shown]
Assuming an annual mortality of 7% in the ICD patient population, the mortality at 5 years is 30% $[1 - (1-0.07)^5]$ In the recent RHYTHM ICD/QuickSite 1056K left heart lead study using CRT-D devices, the annual mortality was 12.8%, which would result in a mortality of 49% $[1 - (1-0.128)^5]$ at 5 years. If the ICD:CRT-D device mix is 60%:40% then the expected overall mortality in this study at 5 years is 38% ($=0.6 \times 0.30 + 0.4 \times 0.49$).

Withdrawals due to reasons other than death

In an ongoing St. Jude Medical post-approval study consisting of CRT devices and LV leads, 102 patients have been withdrawn for reasons other than death during an average of 22 months of follow-up. This translates to an attrition of 22% over 5 years.

Assuming that deaths and withdrawals are independent events, the total attrition is expected to be approximately 52% ($= 1 - (1 - 0.38) \times (1 - 0.22)$) over 5 years. With an expected attrition at 5 years to be 52%, a total of 417 subjects who consent to participate in this sub-study will be enrolled in order to have at least 200 subjects with fluoroscopy data available at the 60 month follow-up visit.

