The expected distribution of ICDs to CRT-Ds in this post-market surveillance study is 3:2³. The annual mortality in the ICD patient population varies between 5.6% and 7%, which are calculated from the published results of the SCD-HeFT and MADIT II trials^{4,5}. Assuming an annual mortality of 7% in the ICD patient population, the mortality at 5 years is 30%. In the recent RHYTHM ICD/QuickSite 1056K left heart lead study⁶, the annual mortality was 12.8%, which gives a mortality of 49% at 5 years. Hence the expected overall mortality in this post-approval study at 5 years is 38% ($=0.6 \times 0.30 + 0.4 \times 0.49$).

3. Withdrawal due to Lost-to-follow-up, system explant due to heart transplant/infection, patient/physician request

In the ongoing St. Jude Medical post-approval study consisting of CRT devices and LV leads⁷, out of a total of 1127 enrollments, 102 patients have been withdrawn for reasons other than death during an average of 22 months of follow-up. This translates to an attrition of 22% over 5 years. It is assumed that attrition in the study over 5 years is 22%. This is a conservative assumption since the CRT Device System Post Approval Surveillance study solely enrolled patients indicated for CRT, while this study is expected to enroll patients receiving either a CRT-D or an ICD.

Assuming that deaths and withdrawals are independent events, the total attrition is thus expected to be approximately 52% ($= 1 - (1 - 0.38) \times (1 - 0.22)$) over 5 years. Thus, a minimum of 1725 patients will be enrolled in the post-approval study.

Patient Group

All patients who give consent for the study and undergo an attempted implant of the Optisure lead or had an Optisure lead implanted within 30 days of enrollment will be included in this analysis.

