5.3.9 Time from other visual lead anomalies by each subcategory to clinical intervention

Lead Population

All Optisure leads with other visual lead anomalies (by each sub category).

Analysis:

Time to clinical intervention will be analyzed using the Kaplan-Meier method. The zero time will be the date at which other visual lead anomaly (by each subcategory) was detected. Those patients who experience other visual lead anomaly (by each subcategory) after enrollment but do not experience clinical intervention will be censored 3 years after enrollment in this trial.

5.3.10 Comparison of patients with lead compromise as evidenced by imaging (includes externalized conductors and other visual lead anomalies) to those without lead compromise

Patient Population

All the patients implanted with Optisure leads.

Analysis

Demographic and clinical parameters will be compared between patients who experience lead compromise as evidenced by imaging and those who do not experience lead compromise. Specifically, the variables age, gender, body mass index, lead size, lead model, and implant factors such as venous access site, number of other leads in the vasculature, fixation location in the right ventricle, level of activity (based on functional NYHA class scale I, II, III, IV), level of therapy that patient received (no ATP/shock, ATP or shock) and slack (grades 0, 1, 2, 3, 4 based on the scale described by Ha et al., 2010⁸) in the lead will be used for the comparison. Continuous variables such as age or body mass index will be compared using Student's T-tests while categorical variables such as gender or lead models will be compared using Pearson's Chi-square statistic. Point estimates and p-values will be provided from these analyses.

5.3.11 Comparison of patients with electrical dysfunction to those without electrical dysfunction.

Patient Population

All the patients implanted with Optisure leads.

Analysis

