Demographic and clinical parameters will be compared between patients who experience electrical dysfunction and those who do not experience electrical dysfunction. Specifically, the variables age, gender body mass index, lead size, lead model, and implant factors such as venous access site, number of other leads in the vasculature, fixation location in the right ventricle, level of activity (based on functional NYHA class scale I, II, III, IV), level of therapy that patient received (no ATP/shock, ATP or shock) and slack in the lead (grades 0, 1, 2, 3, 4 based on the scale described by Ha et al, 2010⁸) will be used for the comparison. Continuous variables such as age or body mass index will be compared using Student's T-tests while categorical variables such as gender or lead models will be compared using Pearson's Chi-square statistic. Point estimates and p-values will be provided from these analyses.

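### Sections 5.3.10 and 5.3.11 compare crude ever/never groups, which ignores time at risk, and use Pearson's chi-square, which is unreliable for multi-category factors if events are few

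*Protocol*

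**What the plan says.** Section 5.3.10 compares "patients who experience lead compromise as evidenced by imaging and those who do not experience lead compromise". Section 5.3.11 does the same for electrical dysfunction. The listed factors include lead model, slack (five grades), NYHA class (four levels), age, body mass index and the therapy the patient received.

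The tests are fixed: "Continuous variables such as age or body mass index will be compared using Student's T-tests", and "categorical variables such as gender or lead models will be compared using Pearson's Chi-square statistic". For both sections, "Point estimates and p-values will be provided from these analyses". No small-cell alternative, significance level or time at risk is mentioned.

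The stated population is "All the patients implanted with Optisure leads". Scheduled cinefluoroscopy, however, is confined to the sub-study (section 4.3, Table 3), at 24, 36, 48 and 60 months. For that sub-study "a total of 417 subjects who consent to participate in this sub-study will be enrolled", and for the main study "Thus, a minimum of 1725 patients will be enrolled in the post-approval study". Section 4.3 also states that "the total attrition is expected to be approximately 52" per cent over five years. Section 3.0 lists ten lead models. No expected rate is given for lead compromise or electrical dysfunction.

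**The concern.** There are two separate problems.

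**Time at risk.** Whether a patient is ever seen with compromise depends on how long the patient stays and, for imaging outcomes, on reaching month 24. A factor tied to survival or withdrawal will then differ between the groups even if it has no bearing on the lead. Therapy received is a special case: it accrues after implant, so longer follow-up raises both the chance of therapy and the chance of a recorded event.

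**Sparse tables.** Electrical dysfunction counts only leads taken out of service, so events may be few. Spread over ten models or five slack grades, expected counts could fall well below 1, where Pearson's approximation is unreliable.

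At stake is whether a reported p-value or point estimate for a lead model or implant factor reflects the lead or is an artefact.

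**Working it through.** **1. The plan's own figures reproduce.** Five-year mortality is 1 − 0.93⁵ = 30.4% (ICD) and 1 − 0.872⁵ = 49.6% (CRT-D). Mixed 60:40, that is 38.1%. Attrition is 1 − (1 − 0.381)(1 − 0.22) = 51.7%, stated as about 52%. Then 200/0.48 = 416.7, so 417, and 828/0.48 = 1725.

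**2. Patients gone before the first scheduled image.** Annual retention against withdrawal is 0.78^(1/5) = 0.9515, or 0.905 over two years. Two-year survival is 0.6 × 0.93² + 0.4 × 0.872² = 0.519 + 0.304 = 0.823. Retained: 0.823 × 0.905 = 0.745. So about 25% leave before month 24, roughly 106 of 417.

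**3. Crude risk under equal hazards.** Assume 0.01 events a year in both groups, close to the 0.0103 complication rate in Appendix D, with 22% five-year withdrawal. The two mortality rates are the protocol's ICD and CRT-D figures. Device type is not a listed factor, so this only illustrates the mechanism.

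- Electrical: risk = λ/(λ+μ) × [1 − exp(−5(λ+μ))], where μ = −ln(1 − annual mortality) − ln 0.9515, giving 0.122 and 0.187. Crude risks are 3.66% and 3.18%, ratio 0.87.
- Imaging: risk = Σ [S(previous visit) − S(t)] × sᵗ over t = 2, 3, 4, 5 years, where S(t) = exp(−0.01t) and s = annual retention (0.885 and 0.830). Crude risks are 3.34% and 2.75%, ratio 0.83.

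The group with higher mortality looks protected although the true ratio is 1.

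**4. Listed factors.** In simulations with no true association and five-year risks of 1 to 5%, therapy received (any against none, assumed 8% a year) was falsely significant in 6.4 to 13% of trials at N = 417, and about 9 to 25% at N = 1725. For age, with an assumed mortality hazard ratio of 1.04 per year, the t-test rejected in 4.1 to 7.7% at N = 417. This bias grows with the number of events.

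**5. Size of Pearson's test.** Events were placed at random among 417 patients, with 40,000 draws per setting and an assumed two-sided 5% level. Assumed shares: models 30, 22, 15, 10, 8, 6, 4, 2, 2, 1%; slack grades 2, 18, 60, 18, 2%.

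| Events | Ten models, uneven | Five slack grades, skewed | Ten models, equal |
|---|---|---|---|
| 2 | 12.6% | 8.0% | 8.5% |
| 4 | 10.5% | 16.5% | 3.6% |
| 6 | 11.0% | 7.3% | 4.6% |
| 10 | 8.1% | 5.0% | 3.2% |
| 14 | 7.1% | 7.8% | 4.9% |
| 43 | 5.7% | 5.3% | 4.7% |
| 61 | 5.3% | 5.3% | 4.8% |

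At 10 events the expected counts across the uneven models are 3.0, 2.2, 1.5, 1.0, 0.8, 0.6, 0.4, 0.2, 0.2 and 0.1: all below 5, six below 1. Other assumed shares gave up to about 20% in the sparsest case.

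Two-level factors are erratic but mostly near or below 5%. One exception is an even split at exactly four events: all four on one side gives a statistic of 4 × 417/413 = 4.04, above 3.84, with probability about 2 × 0.5⁴ = 12.5%.

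Student's t-test with 2 to 20 events against the rest had size 4.6 to 5.2%.

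**6. Which event counts are plausible.** Borrowing the 3.5% complication rate as a five-year risk gives about 10 events in 417 after attrition and 43 in 1725. At 5% the figures are about 15 and 61. The 0.01 hazard in step 3 implies about 13 to 14 in 417.

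**The case against.** The strongest reply is that sparsity is the reviewer's assumption. The protocol gives no rate for these outcomes, and the category shares are invented. With equal model use the inflation is mostly gone from four events on. If the stated population of all implanted patients is taken literally, 43 to 61 events would leave Pearson close to 5%. This stands, and it makes the chi-square half conditional. It does not touch the time-at-risk half, which worsens as events accumulate.

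A reader might infer that t-tests are also inflated by the small event group. The simulated size shows they are not; their only fault is the ever/never grouping. A reader might also take the 0.87 and 0.83 ratios as bias in a planned comparison. They are not: device type is not listed, and a test on it would reject only about 2 to 5% of the time at N = 417 for risks of 1 to 5%.

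These comparisons carry no decision rule, and identifying risk factors is not among the section 2.0 objectives. Time at risk is handled where incidence and progression are estimated: annual hazard rates in 5.3.1 to 5.3.3, and Kaplan-Meier in 5.3.5, 5.3.6, 5.3.8 and 5.3.9. That limits the consequence.

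Finally, an exact-test fallback could sit in an analysis plan that is not shown. The protocol nevertheless names Pearson's test and the crude grouping outright, so this is a stated choice and not an omitted detail.

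**Conclusion.** The point holds as a cheap improvement to exploratory sub-study comparisons.

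- **At any event count:** ever/never status ignores time at risk. On the protocol's own attrition, about 25% of patients leave before their first scheduled image and would count as without compromise. Equal hazards can show crude ratios near 0.87 and 0.83. Therapy received is the listed factor most exposed.
- **Only if events are few and categories uneven:** with an assumed 2 to 10 events in 417, Pearson's size for lead model and slack is roughly 5 to 16% under the tabulated shares. It is about 7 to 8% at 14 events and close to nominal near 40 to 60.
- **Population:** taking all implanted patients for an imaging outcome adds 1725 − 417 = 1308 patients without scheduled imaging, who could be counted as uncompromised.

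The documents do not support saying that the outcomes are known to be very sparse, that every p-value is inflated, or that the primary endpoint is affected.

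**What to change.** In 5.3.10 and 5.3.11:

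1. Compare factors on time since implant, by log-rank or Firth-penalised Cox regression. For imaging outcomes, seen only at 24, 36, 48 and 60 months, use a discrete-time or interval-censored form. Enter therapy received as a time-dependent covariate.
2. Where a contingency-table test is kept, use the Fisher-Freeman-Halton exact test when expected counts are small. This cures sparsity only and does not replace item 1.
3. Limit 5.3.10 to patients with adjudicated imaging. Images from outside the sub-study, such as those taken at system revision (section 9.3), come from a selected group and are best shown separately. State the population of 5.3.11 to match section 19.2, which adjudicates electrical dysfunction in the sub-study.

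The cost is a change of wording and a little more analysis, with no new data collection. Exact tests are slightly conservative with few events.

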2.0 Purpose

The purpose of this post approval study is to characterize the chronic performance of the SJM Optisure family of HV leads in patients that have an approved indication, as per ACC/AHA/HRS/ESC guidelines, for implantation of an ICD or CRT-D system for treatment of heart failure or life-threatening ventricular tachyarrhythmia, and who meet all the inclusion/exclusion criteria. The Optisure lead study will be performed in compliance with the Conditions for Approval as agreed upon with the FDA. If during the course of the study a future generation of the Optisure RV lead is approved, these devices may be included in the study upon agreement with the FDA.

The following objectives will be evaluated in the post approval study:

1. To determine the Optisure lead related complication free rate at 5 years
2. To document all Optisure lead related adverse events

Additionally, the following objectives will be evaluated in a subset of patients in the Optisure lead study who agree to participate in a sub-study:

1. To determine the incidence of externalized conductors after enrollment
2. To determine the incidence of other visual lead anomalies by each subcategory per Appendix A after enrollment
3. To determine the incidence of electrical dysfunction[§] after enrollment
4. To evaluate the 30-day adverse event rate associated with lead revision procedures (include lead extractions or abandonments with or without lead replacement)
5. To determine the prevalence of “other insulation anomalies” in returned Optisure leads:
 - Internal abrasion short under RV shock coil
 - Internal abrasion short under SVC shock coil
 - Exposed conductors defined as a breach of the outer insulation and/or breach of the internal silicone lumen tubing, but the conductor cable is contained within the lead body diameter.

[§]”Electrical dysfunction” is determined to be present after adjudication of the following cases of potential electrical failures that led to the lead being either surgically capped/extracted or electrically abandoned. Potential electrical failures include the following:

- Presence of non-physiologic noise not due to external interference
- Rise in pace/sense (p/s) conductor impedance to $> 2000 \Omega$ or increase of more than 200Ω over previous 6 months or increase of 400Ω over any period of time
- Decrease of more than 200Ω over previous 6 months or to impedance $< 200 \Omega$ from baseline impedance $> 300 \Omega$ or decrease of 400Ω over any period of time

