- **Lead Fracture:** A break in a conduction cable or coil of a pacing or defibrillation lead typically evidenced by an increase in impedance, intermittent or complete loss of capture, intermittent or complete loss of sensing, noise on the intra-cardiac electrogram and rarely, by visual signs of conductor coil fracture on x-ray.
- **Lead Insulation Damage:** A disruption to the integrity of the lead insulation without disruption of the conductor cable(s) or coil observed visually, electrically, or radiographically. An insulation break may be indicated by a drop in impedance, and can cause loss of capture or high voltage therapy delivery or sensing problems.
- **Loss of Capture:** The inability of the device's output pulse to result in depolarization and contraction of the appropriate cardiac chamber. Causes include insufficient stimulus strength, separation of the electrode from the myocardium, some anti-arrhythmic medications and placement of the stimulating electrode in contact with a non-responsive portion of the myocardium such as scar tissue. Delivery of an output pulse at a time when the myocardium is physiologically refractory is not loss of capture, since capture is not physiologically feasible.
- **Loss of Sensing:** A condition in which the pulse generator is unable to sense intrinsic cardiac signals (applicable to RA and RV leads).

- **Observation:** Adverse events that can be managed without invasive intervention (e.g., oversensing or loss of pacing capture, which is remedied by reprogramming of the pulse generator).
- **Oversensing:** The detection of inappropriate electrical signals by the pulse generator's sense amplifier. These signals, such as myopotentials, electromagnetic interference, T waves or crosstalk between atrial and ventricular channels, must be of sufficient duration to interfere with normal device function (applicable to RA and RV leads).
- **Pneumothorax:** An accumulation of air in the pleural cavity due to a disruption of the pleural lining.
- **Re-Attempted Implant:** Implant is being re-attempted in a new procedure due to previous failed implant of the Optisure lead
- **Re-Implant:** Implant is being attempted in a new procedure because of a previous removal of the Optisure lead implanted at enrollment, e.g. due to infection.
- **Successful implant:** An Optisure lead is implanted.

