- Acceleration of arrhythmias (caused by the device)
- Air embolism
- Allergic reaction
- Bleeding
- Cardiac perforation
- Cardiac tamponade
- Chronic nerve damage
- Decompensated heart failure
- Elevated pacing thresholds
- Erosion
- Exacerbation of heart failure
- Excessive fibrotic tissue growth
- Extracardiac stimulation (phrenic nerve, diaphragm, chest wall)
- Failure to detect VT/VF
- Fluid accumulation
- Formation of hematomas or cysts
- Generator malfunction
- Hemothorax
- Inappropriate shocks
- Infection
- Lead/port damage
- Lead fracture
- Lead insulation damage
- Lead migration/dislodgement
- Lead Noise
- Loss of capture
- Failure to deliver therapy
- Loss of sensing
- Myocardial Infarction (MI)
- Oversensing
- Pectoral Stimulation
- Pericardial Effusion
- Pneumothorax
- Thromboemboli
- Undersensing
- Venous occlusion

Patients susceptible to frequent shocks despite antiarrhythmic medical management may develop psychological intolerance to an ICD or CRT-D system that may include the following:

- Dependency
- Depression
- Fear of premature battery depletion
- Fear of shocking while conscious
- Fear that shocking capability may be lost
- Imagined shocking (phantom shock)

For unexpected failure modes or unexpected adverse events, the site should follow their standard reporting practices for medical device reporting (MDR). As defined in 21 CFR 803, a MDR reportable event (or reportable event) means: An event that device user facilities become aware of that reasonably suggests that a device has or may have caused or contributed to a death or serious injury. A device user facility must report deaths and serious injuries that a device has or may have caused or contributed to, establish and maintain adverse event files, and submit summary annual reports to FDA.

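### Section 5.3.11 compares ATP/shock therapy over an undated period between patients with and without electrical dysfunction, so therapy before lead failure is mixed with therapy that the failing lead triggered or prevented

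*Protocol*

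**What the plan says.** Section 5.3.11 states that demographic and clinical parameters will be "compared between patients who experience electrical dysfunction and those who do not experience electrical dysfunction". It names eleven variables. One is "level of therapy that patient received (no ATP/shock, ATP or shock", a three-level category (none, ATP, shock). On method, "categorical variables such as gender or lead models will be compared using Pearson's Chi-square statistic", and on output, "Point estimates and p-values will be provided from these analyses". The section gives no period over which therapy is counted. Section 5.3.10 lists the same variable for lead compromise seen on imaging.

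Section 2.0 defines electrical dysfunction by adjudication of "potential electrical failures that led to the lead being either surgically capped/extracted or electrically abandoned". The first of its five listed failures is "Presence of non-physiologic noise not due to external interference". The other four are changes in pacing impedance (up or down), high voltage impedance or capture threshold.

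Section 4.2 gives electrogram noise as a sign of lead fracture, and says that oversensed signals "must be of sufficient duration to interfere with normal device function". Section 11.0 includes lead noise, oversensing and "Inappropriate shocks" among the possible adverse events.

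**The concern.** Most of the eleven variables are fixed at or near implant. Therapy received is not: it accrues during follow-up, including while the lead is failing. A lead that produces noise can cause the device to deliver ATP or shocks. A lead that has lost sensing or high voltage delivery can prevent them. In both cases the therapy category partly records the outcome and not something that came before it.

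The way dysfunction is dated makes this worse. It is established only after the lead is capped, extracted or abandoned, so therapy driven by a failing lead comes before the recorded outcome. Even an informal rule of counting therapy before dysfunction would let it in.

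Section 4.5 sends sub-study results to FDA in the progress reports. A p-value for therapy level could be taken there as evidence about what makes leads fail. A true effect of delivered therapy on lead integrity, if there is one, could not be separated out.

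**Working it through.** The protocol gives no sample size, expected rate or significance level for this comparison, so there is no planned figure to reproduce. The check is a reading of the text followed by illustrative arithmetic.

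**Paths in the text**

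- *Upward.* Noise is a dysfunction criterion (2.0), oversensing interferes with device function (4.2), and inappropriate shocks are a listed event (11.0). Therapy caused by the lead adds to the count in cases.
- *Downward, device.* Insulation damage can impair high voltage therapy or sensing (4.2). Failure to deliver therapy counts as abnormal lead performance (5.1.1), and failure to detect VT/VF and undersensing are listed events (11.0).
- *Downward, time.* A patient whose lead is removed or capped without an Optisure replacement is withdrawn (16.0), so some cases have less time in which to receive therapy.

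**Size of the upward path** (both inputs assumed, not in the documents)

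Let 25% of patients in both groups receive ATP or shock for reasons unrelated to the lead, and let noise trigger therapy in a share q of cases. Therapy has no effect on the lead.

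- Treated share in cases = 1 − (1 − 0.25)(1 − q)
- Odds in non-cases = 0.25/0.75 = 1/3

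| q | Treated share, cases | Odds ratio |
|---|---|---|
| 0.20 | 0.40 | (0.40/0.60) × 3 = 2.0 |
| 0.40 | 0.55 | (0.55/0.45) × 3 = 3.7 |
| 0.60 | 0.70 | (0.70/0.30) × 3 = 7.0 |

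**Adding the time path** (further assumption: cases are followed for half as long as non-cases, with a constant background rate)

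The background share untreated in cases becomes √0.75 = 0.866, so the treated share is 1 − 0.866(1 − q).

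- q = 0: 0.134, odds ratio (0.134/0.866) × 3 = 0.46
- q = 0.20: 0.307, odds ratio (0.307/0.693) × 3 = 1.33
- q = 0.40: 0.480, odds ratio (0.480/0.520) × 3 = 2.8

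The odds ratio is 1 where 0.866(1 − q) = 0.75, that is at q = 0.13. Below that the bias is downward and above it upward, with no true effect in either case.

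**Effect on the p-value**

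A simulation of the 2×3 chi-square used the sub-study target of 417, equal follow-up, no effect of therapy, 4,000 runs per setting and a 0.05 threshold. Assumed inputs were 30% background therapy (half ATP, half shock), with a share q of cases moved to shock by noise. Dysfunction in 2% or 5% means 0.02 × 417 ≈ 8 or 0.05 × 417 ≈ 21 cases.

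| Dysfunction | q = 0 | q = 0.25 | q = 0.50 |
|---|---|---|---|
| 2% | 4.8% | 33% | 74% |
| 5% | 4.2% | 58% | 97% |

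The entries are the percentages of runs with p < 0.05. The q = 0 column is what remains when only therapy before onset is counted over equal time, and it is close to nominal. The 5% row is generous: section 5.1.1 assumes 95% freedom at five years from all RV lead complications combined.

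**The case against.** The strongest reply is that the time window for one covariate in an exploratory comparison belongs in a statistical analysis plan, which is not shown here. A plan could indeed supply it. But the protocol already fixes the variable, the grouping, the test and the p-value, and therapy received, read as written, includes therapy during lead failure. The point is that the specified comparison cannot be interpreted, not only that detail is absent.

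A reader might infer that a positive association is built in and that the report would present shocks as a cause of lead failure. The documents support neither. Noise is one of five criteria, and impedance or threshold changes need not trigger therapy. No sentence says outright that lead noise triggers ATP or shocks; the link is inferred from the definitions and the adverse event list. The failure-to-deliver and withdrawal paths point the other way. The protocol says only that parameters will be compared, and no section 2.0 objective concerns risk factors. What stands is that the direction is unknown, so a difference or its absence says little about therapy as a risk factor.

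It is also fair that the sizes above rest wholly on assumed inputs. Section 5.3.11 names all patients implanted with Optisure leads as its population, but section 19.2 adjudicates dysfunction only in the sub-study, so 417 is the relevant scale.

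Finally, sorting every episode in every patient into appropriate and inappropriate therapy would be a new task. It would also discard real exposure, since a shock caused by T-wave oversensing still passes through the lead. A date limit deals with reverse causation without that.

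**Conclusion.** The point holds as a modest one. Section 5.3.11 mixes therapy that preceded the electrical failure with therapy that the failing lead triggered or prevented, over follow-up that can differ between groups. The result can be biased upward or downward, upward if noise-triggered therapy dominates, and cannot be read as identifying a risk factor.

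The odds ratios (0.46 to 7.0) and rejection rates (33% to 97%) show that the distortion can be large. They depend on assumed background therapy, noise shares, dysfunction rates and follow-up, and are not estimates for this trial.

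In section 5.3.10 the problem is less direct, because the outcome is an imaging finding and not an electrical one. The variable can still include therapy after the anomaly was seen. The primary endpoint is not affected.

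**What to change.** In section 5.3.11, count only ATP or shock delivered before the first stored episode or measurement that shows the electrical abnormality. For comparison patients, count therapy over the same time since implant, or treat therapy as a time-dependent covariate. Describe therapy at or after that date separately, as a consequence of dysfunction. In section 5.3.10, count only therapy before the first image showing the anomaly. No appropriate/inappropriate classification of all episodes is needed.

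The data are already collected: session records with stored IEGMs are uploaded at enrollment and follow-up (9.2.1, 9.4), and the electrical committee already reviews them for leads taken out of service (19.2). The cost is revised wording, a little programming and slightly fewer exposed cases. One limit remains: the first record or image can come later than the true onset, most of all in 5.3.10, where scheduled imaging is at 24, 36, 48 and 60 months.
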